6.4. Compensation

We will provide \$25 for each semi-structured interview before treatment, after four months, and after eight months of treatment for a potential total of \$75. This is in addition to compensation for completion of tasks of protocol 2015-0366 which are \$25 for emotion testing before treatment and again after four months.

7. Activities and measurements

Enrollment: Participants will be enrolled after signing the informed consent form.

Pre-treatment visit: During the initial visit, the multi-disciplinary clinical team (therapist and surgeon) will provide education on eye care and avoidance of other therapies that could worsen the synkinesis before treatment is initiated (e.g. maximal effort exercises), and describe treatment with neuromuscular retraining therapy and chemodenervation with botulinum toxin injections. Both treatments are standards of care and will be presented without bias as options. After the clinical evaluation, the Study Coordinator will offer study enrollment, obtain consent and assign cohort based on randomization. We will use a predetermined and blind randomization sequence designed independently by the study biostatistician.

		per standard protocol			
Time Window	6 weeks-24 hours before treatment	Four months	After four months	Four months	After four months of dual therapy
Facial Clinimetric Evaluation (FaCE) Scale (10 min)	SOC	SOC	SOC	SOC	SOC
Sunnybrook Facial Grading System (SFGS)	SOC	SOC	SOC	SOC	SOC
Synkinesis Assessment Questionnaire (SAQ) (10 min)	SOC	SOC	SOC	SOC	SOC
Interviews (Audio Recorded) (60-90 min)	X		X		X
Psychological Assessments (HADS, BIPQ) (10 min)	E		E		X
Tasks from Protocol 2015-0366 (60-90 min)	E		E		

Procedure Key: **SOC** = performed as needed per Standard of Care; **X** = Research Only for this protocol; **E** = Research only for Protocol 2015-0366

7.2. Data entry

Data will be collected electronically. The following will be captured electronically: (1) data from the electronic medical record (see data collection sheet); (2) evaluation video and audio recordings and clinician reports/summaries; (3) audio recordings of participant interviews and electronic codes for content themes. Paper data collection may consist of the FaCE, SAQ, BIPQ, and HADS. Raw data will be scored or otherwise evaluated as necessary and entered into a REDCap database as soon as possible after data collection.

Video recordings collected during this study will not be immediately destroyed after all research procedures have been completed, as this data is collected as part of clinical care and could be of value to a follow up or related study. Subjects will have the opportunity to consent to their data being used in future studies. IRB approval will be sought for any use of this data outside of the study parameters described in this protocol.

7.3. Participant withdrawals

Participants have the right to withdraw from the study at any time for any reason, either before or after treatment begins. Additionally, any participant may be discontinued from the study at any time at the discretion of the investigator if he or another provider feels it is in the best interest of the participant. If a participant withdraws or is withdrawn from one aim, they may continue to participate in the other aims.

Study participation may be terminated early under the following circumstances:

- (1) the participant does not meet all inclusion criteria and is deemed a screen failure
- (2) the participant meets any of the exclusion criteria and is deemed a screen failure
- (3) the participant does not adhere to protocol requirements (e.g., completing questionnaires, refusing permission to have interview recorded, etc.)
- (4) the participant experiences an AE which in the investigator's opinion requires their withdrawal from the study
- (5) the participant is lost to follow up
- (6) death of the participant

The study team will document the reason(s) for withdrawal of each participant in source documents.

Participants that withdraw or are withdrawn prior to treatment will be replaced. Their pre-treatment data may be used to establish baseline function for comparison. Participants that withdraw from any aspect of the study will continue to be cared for per the standard of care.

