2.1. Primary outcome and endpoints

To determine improvement in physical functioning from baseline, we will look at the change on the clinician-reported Sunnybrook Facial Grading System (SFGS). The examination is routinely collected at clinic visits. At each clinic visit, patients will be videotaped as a part of routine care. However, patients in the study will undergo a blinded evaluation and SFGS scoring using the video by trained blinded clinicians not participating in their direct clinical care, to decrease observer bias.

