Participants will be primarily identified from our University of Wisconsin *Facial Nerve Clinic*. While most patients with facial nerve paralysis recover in 3 months, patients with chronic facial paralysis may still benefit from spontaneous recovery of muscle function thereafter. Symptoms of synkinesis are often not displayed until 4 months with the display of aberrant facial muscle motions. Eligible patients will demonstrate synkinesis and had their onset of peripheral facial paralysis from any cause at least 4 months prior. Muscle function and synkinesis will be assessed using standard clinical evaluation tools.

Exclusion criteria: (1) under 18 years of age (2) previous treatment with reanimation surgery (except for those patients who underwent upper eyelid weight placement to aid in eye closure), (3) intolerance or contraindication to botulinum toxin injection, and/or (4) previous treatment for synkinesis with chemodenervation or neuromuscular retraining therapy (5) vulnerable populations such as known prisoners, pregnant/breastfeeding women, or subjects with impaired decision-making capacity, including those with severe psychiatric illnesses (6) individuals over 89 years of age

Pre-Treatment Screening and Testing: Pre-treatment activities will include clinical evaluation and clinician- and patient-reported instruments that are already standard of care (SFGS, SAQ, FaCE), a semi-structured interview, and the tasks included in IRB Protocol 2015-0366. Patients will be randomly assigned to one of two treatments; Arm 1: neuromuscular retraining therapy for four months, with chemodenervation added thereafter, or Arm 2: Botox/chemodenervation for four months, with neuromuscular retraining therapy added thereafter. Allocation schedule will not be known to clinicians prior to consenting.

Blinding: Research team members who will score the videos will be blinded. The physician conducting the initial clinic visit will be blinded to the patient's treatment arm until after they have been enrolled. The physician providing treatment, interviewer, and study coordinator will not be blinded to the participant's treatment arm.

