8.3. Analysis of endpoints

To reduce the risk of bias, two Department of Surgery research employees will independently grade videos and photos in a blinded fashion using the Sunnybrook Facial Grading System instrument. Video recordings will be presented in random order to two trained research assistants. Ten percent of samples will be included twice to measure intra-rater reliability. Twenty percent of samples will be re-scored by the other rater to measure inter-rater reliability. [name] will be responsible for rater training prior to the investigation, and during the study [name] will provide independent oversight, ongoing training, and resolution of scoring disagreement. At the conclusion of the study, study biostatistician [name], who generated the randomization sequence, will perform data analysis comparing mean changes between groups and account for participant drop out if necessary.

Our qualitative analysis will proceed concurrently with data collection to allow identified themes to be explored in subsequent interviews. In qualitative research this involves both coding the written transcripts and then modeling the coded data. All team members will analyze the data and look for themes and trends that are emergent from the data. For the pre-treatment interviews, we will employ Conventional Content Analysis¹⁵ which will allow us gain direct information from study participants without imposing preconceived categories or theoretical perspectives. For the post-treatment interviews, we will switch to directed content analysis as the findings from pre-treatment interviews will guide our analysis of post-treatment interviews, while capturing emergent themes that come up in the data. We will establish reliability in our analysis through peer debriefing, triangulation, and expert feedback (through [name]), and member checks. Coded transcripts, the codebook, and descriptions of codes will be maintained using NVivo 11 software (QSR International). As coding evolves, changes will be documented in an audit trail. We will map our findings onto the PROMIS measures; specifically, Social

Functioning and Social Isolation scales, to determine the domains that are important to patients but are not included in current quantitative measures.

9. Risks and benefits of trial participation

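### Section 7.3 ends study participation, not just assigned treatment, when a treated patient is withdrawn for harm or best interest, which permits informative loss of the 4-month SFGS that the section 8.1 model does not correct

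*Combined protocol and SAP*

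**What the plan says.** Two clauses in section 7.3 can remove a patient after treatment has begun. The first is discretionary: "any participant may be discontinued from the study at any time at the discretion of the investigator if he or another provider feels" that this serves the participant's best interest. The second is item (4) in the list of reasons for ending participation early: "the participant experiences an AE which in the investigator's opinion requires their withdrawal from the study". Both refer to leaving the study. Neither describes a patient who stops the assigned treatment and remains under observation.

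Other text that bears on the point:
- Section 7.3 lets someone withdrawn from one aim continue in the others, and replaces only those who leave before treatment. It also says "Participants that withdraw from any aspect of the study will continue to be cared for per the standard of care".
- Section 3 (Blinding) says "The physician providing treatment, interviewer, and study coordinator will not be blinded to the participant's treatment arm", but also "Research team members who will score the videos will be blinded".
- Section 2.1 says of the SFGS recordings: "At each clinic visit, patients will be videotaped as a part of routine care".
- Section 8.1 fits a random effects model to baseline and 4 months. The treatment effect is the group-by-time term. No analysis population is defined.
- On missing outcomes, section 8.3 says only that the analysis will "account for participant drop out if necessary".

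**The concern.** The two clauses are triggered by harm or by a provider's judgement that the patient should leave. Either can be related to how the patient is doing. The judgement can be made by someone who knows the arm, and section 9.1 lists different harms for injection and for retraining. During the first four months the trial holds each patient to one treatment, whereas section 1.2 says usual practice at the centre is one or both, by clinician judgement and patient preference. Leaving the study is therefore a possible route to the other treatment for a patient who is not improving.

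Nothing says that such a patient's 4-month SFGS is still obtained, scored or analysed in the randomised arm. If it is not, the primary contrast moves from all randomised patients towards those who stayed on each treatment. Blinded scoring does not help when there is no score. The one-aim clause does not help either, because the SFGS is the Aim 1 primary outcome. With 18 per arm, a few patients matter.

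**Working it through.** **Inputs.** From section 8.2: 18 per arm, 7-point difference, SD 7.1, planning correlation 0.5, 10% loss (36 × 0.10 = 3.6, about 4 patients), power about 80%. Assumed, because not stated: two-sided alpha 0.05. I read 7.1 as the SD at each time point. The biases below scale in proportion to the SD of change.

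**1. The plan's own figure.** SD of change = 7.1 × √(2 × (1 − 0.5)) = 7.1. After 10% loss, 18 × 0.9 = 16.2 per arm. Standard error = 7.1 × √(2/16.2) = 2.49. 7/2.49 = 2.81, and 2.81 − 1.96 = 0.85, so power is 80.1% (79.6% with 16 per arm). The stated 80% is reproduced. This allowance protects power if loss is random. It says nothing about bias.

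**2. Bias if scores are lost.** The documents give no withdrawal rates by arm and no outcomes for withdrawn patients, so these are scenarios. I simulated 18 per arm, lost about 4 of 36, and compared change scores by t-test (20,000 runs each).

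| Loss | Bias (points) | Type I error | True 7 estimated as |
|---|---|---|---|
| 4 at random, any split | 0 | about 5% | 7.0 (power 76–77%) |
| Worst 2 changes in each arm | 0 | 8% | 7.0 |
| 4 from one arm, at random from its worse half | 1.5 | 8% | 5.5 or 8.6 |
| Worst 4 changes, all from one arm | 2.6 | 20% | 4.4 or 9.6 |

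The bias favours the arm that loses the patients. Where two estimates are shown, the lower applies if the loss is in the chemodenervation arm and the higher if it is in the retraining arm.

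The last row is extreme. The bias in an arm's mean change is (m/18) × gap, where m patients are lost and the gap is how much worse their mean change is than that of those who remain. With m = 4 and a bias of 2.57, the gap is 2.57 × 18/4 = 11.6 points, or 11.6/7.1 = 1.6 SD.

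**3. Does the section 8.1 model repair it?** Only in part. A patient without a 4-month score still contributes a baseline. At correlation 0.5, the regression of baseline on change has slope (0.5 − 1) × 7.1² / 7.1² = −0.5. Completers whose mean change is 2.57 too high therefore have a mean baseline 1.285 too low and a mean 4-month score 1.285 too high. The model adjusts the 4-month mean to 1.285 + 0.5 × 1.285 = 1.93, and the baseline mean over all randomised patients is right. The bias falls from 2.57 to 1.93, which is 0.75 × 2.57.

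Fitting the mixed model to simulated data agrees. With 150 runs per scenario, the bias with no true effect was 1.9, and a true 7 was estimated as 4.4 or 8.9. The 4.4 is low because of simulation noise. Longer runs (1,100 to 1,500 fits each) gave 2.0 with no true effect, and 4.8 or 9.2 for a true 7. The bias in the planned model is thus about 1.9 to 2.2 points in the extreme scenario, with a type I error of about 16%. The model assumes data missing at random, and it contains no intermediate SFGS to make that plausible.

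**4. Range.** 0 to 2.6 points on change scores (2.6/7 = 37% of the planning difference), or 0 to about 2 in the planned model (2/7 = 29%), in either direction.

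**The case against.** A reader might infer that the 4-month comparison will lose its worst outcomes, and lose them unequally by arm. The documents do not support that. The clauses are permissive. No section says that withdrawn patients' SFGS is excluded, that they would have the poorest change, or that withdrawal would differ by arm. Several harms in section 9.1, such as bruising, headache or soreness, do not imply a poor SFGS. Section 1.2 calls the injection effect temporary, so an early harm need not lower the 4-month score. If loss is unrelated to outcome, or is similar in both arms, the bias is about zero. All of this stands, and it limits the point to what the rule permits.

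A reader might also infer that the missing scores already exist as routine videos and cost nothing to use. That goes too far. Section 9.2 says injection patients are not seen between treatments, section 3 allows evaluation by phone, and the key to Table 1 makes standard-of-care assessments as needed. Some patients who stop injections may have no 4-month clinic video unless one is scheduled.

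Lastly, the discretion clause has legitimate uses beyond treatment, such as taking a distressed participant out of interviews, and section 7.4 gives the safety committee its own power to remove individuals. A remedy that allowed only withdrawal of consent, loss to follow-up or death to end data collection would override these.

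What does not stand is the reply that 10% loss is already planned, or that drop-out will be accounted for. The first covers power only, and the second names no method.

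**Conclusion.** The concern holds as a weakness of the rule, not as a prediction of its effect. Section 7.3 joins stopping treatment to leaving the study for reasons that may be tied to outcome, at the discretion of people who may know the arm. No retention rule, analysis set or missing-data method guards the primary outcome. The possible bias is 0 to about 2.6 points on change scores, or up to about 2 points in the planned model, against a planning difference of 7. The upper end rests on assumptions that the documents neither state nor exclude: about 4 of 36 lost, all from one arm, all with that arm's worst changes, and an SD of change of 7.1. The change is worth making because it is cheap and protects the primary contrast.

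**What to change.** In section 7.3, state that when the discretion sentence or item (4) is used after treatment has started, stopping the assigned treatment does not by itself end follow-up. Unless the participant withdraws consent for it, the 4-month SFGS video, with SAQ and FaCE, is still sought. The video is scored by the blinded raters, and the data are analysed in the randomised arm.

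Leave unchanged the clinical decision to stop treatment, the power to stop interviews or other research procedures, removal by the safety committee, and items (1) to (3).

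In section 8, replace the general promise about drop-out with a pre-specified missing-not-at-random sensitivity analysis for 4-month scores that are still missing. One form is to shift the missing values by a range of amounts, separately by arm, and report where the conclusion changes.

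The cost is protocol and consent wording, a short addition to the analysis plan, and an occasional scheduled 4-month video for injection patients otherwise followed by phone. Some scores will come from patients who stopped or changed treatment, which may dilute the difference slightly.

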AIM 2: Determine the social, emotional, and functional burden of synkinesis, not captured in current patient-reported outcome measures as well as effect of treatment. We will analyze qualitative interviews with individual patients collected before treatment, after four of treatment, and after eight months of treatment to study the burden of disease, experience with treatment, and potential differences in both treatments. Our primary outcome is to identify the domains that may be missing from existing patient-reported measures collected in AIM 1. To do this, we will compare findings to assessment domains (i.e. decreased engagement, negative mood, etc.) in the FaCE, SAQ, and the two disease non-specific instruments, HADS and BIPQ. We will then evaluate our findings based on domains in PROMIS measures, an NIH-supported collection of validated and standardized scales.

AIM 3: Quantify the disruption in social functioning caused by synkinesis using innovative social-perceptual outcomes and emotion recognition tasks. Prior to treatment, participants will enroll in IRB Protocol 2015-0366 and complete a series of social functioning and mental health instruments and emotion expression recognition tasks. Results will be compared to control subjects without facial disability to reveal the social-perceptual impairment attributable to synkinesis. Repetition of these tasks after four months of either treatment may show improvement in recognition and emotional information interpretation when compared to initial measurements.

Figure 1: Trial overview diagram

[figure not shown]

Table 1. Schedule of activities

	Pre-treatment	Phase I	Study midpoint	Phase II	Study concludes
	Screening	Therapy or chemodenervation per standard protocol	4-month evaluation	Pragmatic trial with dual therapies	8-month evaluation
Window	>6 weeks after onset of paralysis-24 hours before treatment	Routine visits over four months	After four months	Routine visits over next four months	After four months of dual therapy
Informed Consent Obtained	X				
Randomization	X				
Enrolled	X				
Clinical Evaluation	SOC	SOC	SOC	SOC	SOC
Interviews (Audio Recorded)	X		X		X
Adverse Events Monitoring	X		X		X
Assessment of Facial Movement, Paralysis & Well-Being					
Facial Clinimetric Evaluation (FaCE) Scale (10 min)	SOC	SOC	SOC	SOC	SOC
Sunnybrook Facial Grading System (SFGS) [Video]	SOC	SOC	SOC	SOC	SOC
Synkinesis Assessment Questionnaire (SAQ) (10 min)	SOC	SOC	SOC	SOC	SOC

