5.3. Allocation to intervention

Participants will be randomized to each treatment arm with equal probability (1:1 randomization) using a computerized random number generator with random block size (all study personnel except the statisticians are blinded to block size). The randomization assignment will be revealed to the unblinded study coordinator after consent. The clinicians will be blinded to the treatment until the end of clinic.

6. Participant recruitment and consent

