6.3. Recruitment and consent

The human subjects participating in this study will be recruited from the University of Wisconsin *Facial Nerve Clinic*. After physicians identify eligible patients and introduce available treatments, they will ask if the patient is interested in speaking to a study coordinator. A study coordinator will then offer enrollment in both IRB protocol 2015-0366 and this protocol. In clinics where the study coordinator is not available, patients will be given an information sheet, flowchart, and consent form describing the study during the patient's visit at UWHC and told that the coordinator will call within the week to explain the study.

A participant's decision whether or not to participate will not affect the care received as a patient. Participants will be treated according to the standard of care until consent for the study is obtained. Participants must meet inclusion and exclusion criteria as listed above. Participants will be selected without consideration of socio-economic background, however if their insurance status precludes them from coverage for therapy and/or Botox they will need to pay out of pocket. If they are unwilling/unable to do this, we will not enroll them in the study as their treatment with only the treatment covered by insurance would not be truly random.

Following explanation of the consent form, each potential participant will be given an opportunity to read it thoroughly. Before being allowed to sign the consent form, potential participants also will be given an opportunity to ask questions. The investigator will emphasize the fact that the participant can terminate involvement at any time without any consequences. Once the consent form has been signed, the study pre-treatment procedures will be performed if not already captured in the medical record.

A participant is enrolled prior to treatment and will undergo baseline evaluations. They will be randomized on the day of their initial clinic visit.

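### Section 7.3 replaces people who leave a known arm before treatment, and Section 8 does not keep them in the 4-month comparison

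*Combined protocol and SAP*

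**What the plan says.** **Timing of assignment.** Section 6.3 says of participants: "They will be randomized on the day of their initial clinic visit". Section 7 has the coordinator take consent and assign the cohort after the clinical evaluation. Section 5.3 adds: "The randomization assignment will be revealed to the unblinded study coordinator after consent", and then: "The clinicians will be blinded to the treatment until the end of clinic". Table 1 lists randomisation in the pre-treatment column, whose window reads "6 weeks after onset of paralysis-24 hours before treatment". Assignment therefore comes before treatment, although the length of the gap is not given.

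**Withdrawal and replacement.** Section 7.3 lets participants leave at any time. It also provides that "any participant may be discontinued from the study at any time at the discretion of the investigator", subject to a provider's view that this is in the participant's best interest. Early termination covers screen failures, for example where "the participant does not meet all inclusion criteria and is deemed a screen failure", alongside adverse events, non-adherence and loss to follow-up. On exits before treatment it says: "Participants that withdraw or are withdrawn prior to treatment will be replaced". On their data: "Their pre-treatment data may be used to establish baseline function for comparison". It requires reasons for withdrawal to be documented.

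**Analysis.** Section 8.1 specifies a linear random effects model with a group-by-time term at 4 months and names no analysis population. Section 8.3 leaves drop-out to be dealt with by the biostatistician if the need arises, without a method. The supplied text contains no intention-to-treat statement.

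**The concern.** Randomisation protects the comparison only while people are analysed in the arm they drew. Section 7.3 does not separate someone who leaves before assignment, or proves ineligible, from someone who leaves because of the arm drawn.

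A reason to leave a known arm is plausible here. The arms ask different things of patients: therapy visits with daily home practice, or injections. Outside the trial the clinic offers one or both treatments by judgement and preference (Section 1.2), and people who withdraw stay in routine care (Section 7.3). Section 9.2 itself foresees patients who would have chosen retraining alone being assigned to injection.

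If exits differ by arm, and those who leave would have improved less, losing their 4-month outcomes makes the arm they left look better. Restoring the count to 18 then gives an apparently complete arm, and nothing in Section 8 asks for the loss to be shown.

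**Working it through.** **Inputs from Section 8.2:** 18 per arm, SD 7.1, correlation 0.5, 10% loss, target difference 7, power about 80%. Two-sided 5% is assumed, because Section 8.2 states no significance level.

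**The plan's own figure.** A per-visit SD of 7.1 with correlation 0.5 gives a change SD of 7.1 × √(2 × (1 − 0.5)) = 7.1. With 18 × 0.9 = 16.2 per arm, the standard error is 7.1 × √(2/16.2) = 2.49. Then 7/2.49 = 2.81, and 2.81 − 1.96 = 0.85, so power is 80.1% (normal approximation). The stated power reproduces. It already allows for 10% loss.

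**Size of the shift (illustration).** Assume k people leave one arm before treatment, would have improved d points less than the rest of that arm, and have no 4-month value in the analysis. The values of k and d are assumptions; d is set at 0.5 and 1 SD.

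- With replacement, 18 start in each arm and 18 + k were randomised to the affected one: shift = k/(18 + k) × d.
- Without replacement, k of the 18 are lost: shift = k/18 × d.

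| k | d | With replacement | Without |
|---|---|---|---|
| 2 | 3.55 | 0.36 | 0.39 |
| 2 | 7.1 | 0.71 | 0.79 |
| 3 | 3.55 | 0.51 | 0.59 |
| 3 | 7.1 | 1.01 | 1.18 |
| 4 | 3.55 | 0.65 | 0.79 |
| 4 | 7.1 | 1.29 | 1.58 |

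In every row the shift is larger without replacement. The lost outcomes cause the bias; added participants dilute it slightly.

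**Scale.** With 16 per arm analysed, the standard error is 7.1 × √(2/16) = 2.51. Shifts of 0.36 to 1.29 are 0.14 to 0.51 of a standard error and 5% to 18% of the 7-point target. With no true effect, the nominal 5% two-sided error becomes 5.2% to 7.9% (noncentral t, 30 df). Simulation that models the other arm as a mixture gives 5.1% at the low end and 7.5% at the high end.

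**Exits from both arms.** With 3 from one arm and 1 from the other, the shift is (3/21 − 1/19) × d = 0.32 to 0.64 points, with error of 5.2% to 5.7%. With equal numbers and the same gap it is zero.

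**The case against.** Several objections stand, and they limit the point.

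- A reader might infer that replacement itself biases the trial. The table shows otherwise: for k = 4 and d = 7.1 the shift is 1.29 points with replacement and 1.58 without.
- A reader might infer that the protocol orders replaced people out of the analysis. It does not say so. Section 8.1 compares the arms, and its model can accept baseline-only records. Exclusion is inferred from the replacement rule, the optional baseline use and the absence of a named population. Even if kept, baseline-only records add almost nothing to the group-by-time term.
- A reader might infer unlimited investigator discretion, or selective removal. The discretion is tied to the participant's best interest, and nothing suggests misuse.
- The gap between assignment and treatment is not quantified. Section 6.3 also allows the coordinator to call within a week, which fits poorly with randomisation on the day of the initial visit.
- Several features lower the risk. Both treatments are described before consent, patients unwilling or unable to pay for uncovered treatment are not enrolled, both arms receive both treatments after month 4, and reasons for withdrawal are recorded.

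None of this settles who is analysed. Blinded video scoring protects the measurement, not the comparability of the arms.

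**Conclusion.** The concern holds as a gap in the rules: Section 7.3 permits exits from a known arm to be replaced, and Section 8 does not keep those randomised people in the comparison. The text does not show that such exits will happen, in which arm, or in which direction they would push the result. On the assumed 2 to 4 one-sided exits with a 3.55 to 7.1 point gap, the effect is small to moderate: about 0.4 to 1.3 points with replacement and somewhat more without. The upper end needs four exits, all from one arm, with a full 1-SD gap. The plan should be changed because the remedy is standard and cheap; the illustration does not show that the result would be wrong. Confidence is medium.

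**What to change.** **Section 7.3.** Limit replacement to withdrawals before the assignment is revealed, or to ineligibility established on information that predates randomisation and judged without knowledge of the arm. State that any later added enrolment takes the next allocation in the sequence and does not remove the earlier participant.

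**Section 8.1.** Define the primary analysis as all randomised participants in their assigned arm, using a 4-month SFGS video for non-starters where one exists and the participant permits it. Make an analysis of those who started treatment a sensitivity analysis, and say how a missing 4-month value is handled. Report pre-treatment withdrawals by arm with reasons.

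**Section 8.2.** State the power effect of keeping non-starters.

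**Cost.** This is mostly wording, plus a consent line on later routine videos. Power may fall by an amount that depends on an unstated rate:

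- If the planned 10% loss covers the early leavers, power stays at 80.1%.
- If kept non-starters dilute the 7-point difference by an assumed 5% to 10%, power is about 76% to 71%. Restoring it needs 18/(1 − f)², that is 19.9 to 22.2, or 20 to 23 per arm after rounding up.
- If 2 to 4 non-starters in one arm contribute none of the 7 points and as many are added by next allocation (n = 18 + k/2 per arm on average, f = k/n, 10% loss), power is about 73% to 66%.

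Some non-starters will still lack a 4-month value, and others may have received either treatment in routine care, so the fix recovers only part of the information.
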